3.7.2.1. Adverse Events of Special Interest

An AE of special interest (AESI) is one of scientific and medical interest specific to understanding the investigational product and may require close monitoring and rapid communication by the investigator to the sponsor. The following are the AESI's defined for the study:

- Suspected or Confirmed Intestinal Perforation
- Complicated Herpes Zoster (multi-dermatomal, disseminated, or with ophthalmic or CNS involvement)
- Malignancy excluding non-melanoma skin cancer
- Non-melanoma skin cancer
- Serious Infection (e.g., that requires hospitalization or intravenous antibiotics)
- Opportunistic Infections
- Thromboembolic disease (e.g. deep vein thrombosis, pulmonary embolism)
- Clinical Laboratory Abnormalities of Concern
- Major cardiovascular Event (e.g. myocardial infarction or cerebrovascular accident)

The incidence of AESI will be summarized overall and by AESI category and preferred term.

3.7.3. Additional Safety Assessments

3.7.3.1. Clinical Laboratory Parameters

Laboratory data, hematology, serum chemistry and urinalysis, will be summarized in terms of observed values and changes from baseline for Induction period and overall separately. In addition, changes from baseline relative to normal ranges from the central lab (e.g., shifts from normal to abnormal high/low) will be summarized.

Summaries for laboratory parameters of special interest will also be presented, these will include:

- Neutrophils
- Leukocytes
- Lymphocytes
- Hemoglobin
- Lipids [LDL cholesterol, HDL cholesterol, Cholesterol, and Triglyceride]
- Liver Function Test's [ALT, AST, Bilirubin]
- Creatinine
- Creatinine Kinase

A summary of maximum National Cancer Institute Common Terminology Criteria for Adverse Events (NCI-CTCAE) toxicity grade (Appendix 5.8) for postbaseline laboratory values through Week 12 and ATE Week 48.

Listings will flag laboratory values that are outside of normal range.

A listing of all abnormal lab values will be provided. Listings of subjects with any abnormal postbaseline laboratory values of CTCAE grade ≥ 2 will also be provided.

3.7.3.2. Vital Signs

Descriptive statistics for vital signs (systolic and diastolic blood pressures, pulse rate, and weight) and changes from baseline values at each visit and at the end of study will be presented by treatment group.

For each nominal time point, vital signs will be summarized in terms of observed values and changes from baseline. Marked abnormalities as defined in Table 8 will be flagged in the listing.

Table 8: Criteria for Marked Abnormalities in Vital Signs

Heart Rate (bpm)	Systolic Blood Pressure (mm Hg)	Diastolic Blood Pressure (mm Hg)
< 40	< 85	< 45
> 110	> 160	> 100

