Sample Size:

Assuming that the less effective TD-1473 dose results in a 45-point improvement in placebo-adjusted CDAI score change at Week 12, the more effective dose results in a 60-point improvement, the residual SD is 100 points, and a sample size of 160 subjects with 60 subjects in each of the active dose groups and 40 subjects in the placebo group, 100,000 simulations performed using SAS/IML software yielded the following power estimates for 2-sided testing with the familywise Type I error rate controlled at 5% using the Hochberg -step-up procedure:

- 82% power to show at least one of the two doses effective
- 58% power to show both doses effective

The target effect size of 60 points was selected as predictive of a clinically significant increase in clinical response rate. Of note, the study is not powered for the secondary endpoints.

Study Efficacy Endpoints:

The primary endpoint is:

- CDAI score change from baseline at Week 12

The secondary endpoints are:

- CDAI clinical response (defined as reduction from baseline of ≥ 100 points or CDAI < 150) at Week 12
- CDAI clinical remission (defined as CDAI < 150) at Week 12
- SES-CD change from baseline at Week 12
- Endoscopic response (SES-CD reduction of $\geq 50\%$ from baseline or endoscopic remission) at Week 12
- SFAP clinical remission defined as abdominal pain score ≤ 1 (on a scale of 0-3), stool frequency ≤ 2.8 , and both not worse than baseline at Week 12

Study Safety Endpoints:

- Changes from baseline in vital signs, ECGs, and clinical laboratory results
- Incidence and severity of AEs

PROTOCOL SYNOPSIS (CONTINUED)

Analysis:

The primary analysis set for efficacy analyses will be a modified Intent-to-Treat (mITT) set: all randomized subjects who received study drug and had at least one postbaseline CDAI score. Efficacy data will be summarized by randomized treatment. The primary analysis set for general and safety analyses will be the Safety set: all randomized subjects who received study drug. Safety data will be summarized by treatment received.

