8. STATISTICAL CONSIDERATIONS

8.1. General Considerations

All data for each subject will be listed as collected. All statistical summaries and analyses will be performed using [REDACTED]

Continuous data will be summarized using an 8-point summary (n, mean, standard deviation [SD], median, interquartile range [25% quartile, 75% quartile], minimum, and maximum) unless otherwise specified in the SAP or table shell. Categorical data will be summarized using counts and percentages.

Study Day 1 is defined as the day of the first study drug dose. The preceding day is Study Day -1.

Baseline is the last assessment (scheduled or unscheduled) obtained before start of study drug dosing, unless otherwise specified in the SAP (e.g., for fecal sample assessments). Baseline for endpoints that have more than one component is calculated from the individual component baselines, whether or not they were assessed during the same visit.

The study will include 2 formal database locks, one after all 160 subjects have either completed or withdrawn from the Induction phase, and one after all subjects have completed or withdrawn from the ATE phase. Separate SAPs will be prepared for the following unblinded analyses, and finalized before the database are locked for analysis:

Database lock after the Induction Phase is completed:

- Analyses of induction data, to include specifications for [REDACTED] [REDACTED] SAP, when not otherwise specified, refers to this SAP)

- [REDACTED]

- [REDACTED]

Database lock after the ATE phase is completed:

- Analyses of ATE data

Any changes to the data summaries and analyses outlined in this section will be described in the applicable SAP. Any major changes to the definition of the primary endpoint will also be included in a protocol amendment.

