8.8. Safety Analyses

Safety data will be summarized by treatment received; specifically, induction safety data will be summarized by treatment received during induction and ATE safety data by treatment received during the ATE. Summaries will be provided by nominal visit and time point or for the entire treatment period, as appropriate for the type of data. Quantitative data collected at unscheduled times will be listed but will not be included in summaries. Categorical data collected at unscheduled times (e.g., ECG finding categories) will not be included in summaries by time point but will be included in summaries of findings during the entire treatment period.

[REDACTED]

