8.8.5. Vital Signs Data

HR, systolic and diastolic BP, respiratory rate, and body temperature values at each visit and time point and changes from baseline at each visit and time point after the first dose will be summarized, and counts and percentages will be shown for the categories in Table 3.

Table 3: Thresholds for Vital Signs

Heart Rate (bpm)	Systolic Blood Pressure (mmHg)	Diastolic Blood Pressure (mmHg)
< 40	< 85	< 45
> 110	> 160	> 100

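### SAP 3.7.3.2 turns the protocol's counts of vital-sign threshold exceedances into listing flags, and its list of summarised parameters does not name respiratory rate or body temperature

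*SAP*

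**What the plan says.** Change in vital signs is a named safety endpoint in the protocol synopsis: "Changes from baseline in vital signs, ECGs, and clinical laboratory results". Protocol 8.8 sets the presentation: "Safety data will be summarized by treatment received". Protocol 8.8.5 then makes two commitments.

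- It summarises "HR, systolic and diastolic BP, respiratory rate, and body temperature values at each visit and time point", together with changes from baseline after the first dose.
- It adds that "counts and percentages will be shown for the categories in Table 3". Table 3 holds six cut-offs: heart rate below 40 or above 110 bpm, systolic pressure below 85 or above 160 mmHg, and diastolic pressure below 45 or above 100 mmHg.

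SAP 3.7.3.2 covers the same ground differently. Its first sentence opens "Descriptive statistics for vital signs (systolic and diastolic blood pressures, pulse rate, and weight", with the bracket closing there, and presents these by treatment group. A second sentence says, without the bracket, that observed values and changes will be summarised at each nominal time point. On the cut-offs it says: "Marked abnormalities as defined in Table 8 will be flagged in the listing". Table 8 (as numbered in the body of the SAP) carries the same six cut-offs as protocol Table 3.

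**The concern.** The two documents give different outputs for the same cut-offs. The protocol produces a number and percentage of subjects; the SAP produces a mark beside individual values in a by-subject listing. A listing can be searched, but it has no denominators and gives no rate per arm.

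Safety and tolerability is one of the two primary objectives. For the other two parts of the same safety endpoint the SAP keeps categorical summaries: numbers and percentages for ECG ranges (SAP 3.7.3.3), and shifts and CTCAE grades for laboratory values (SAP 3.7.3.1). Only vital signs lose theirs.

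The bracketed parameter list raises a second, smaller question. Respiratory rate and temperature are recorded under Protocol 6.4.7 and promised in Protocol 8.8.5, but the SAP does not name them. Temperature has some bearing here because serious and opportunistic infections are adverse events of special interest.

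**Working it through.** There is no plan figure to reproduce, so the check is mainly a comparison of text.

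| Item | Protocol 8.8.5 | SAP 3.7.3.2 | Other SAP output |
|---|---|---|---|
| Systolic <85, >160; diastolic <45, >100 | n (%) | listing flag | minimum and maximum by arm |
| Heart rate <40 | n (%) | listing flag | minimum by arm |
| Heart rate >110 | n (%) | listing flag | maximum by arm; ECG n (%) only above 120 and 130 bpm |
| Respiratory rate, temperature | values and changes | not named | none found |

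**Cut-offs.** All six agree between protocol Table 3 and SAP Table 8. The SAP counts none of the six from vital-sign data.

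**Parameters.** The protocol names five. The SAP bracket names three of them and adds weight, so two of five are unnamed.

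**What ECG data cover.** SAP Table 9 counts heart rate above 120 and 130 bpm and increases above 20 and 30 bpm. It has no low category and nothing for 111 to 120 bpm. Under Protocol Table 1 the ECG in Induction is taken on Day 1 and then at Week 12 (or at an early discontinuation visit), whereas vital signs are also taken at Weeks 4 and 8. The readings also differ in kind. Protocol 6.4.8 has ECGs after 10 minutes supine; Protocol 6.4.7 has vital signs after 5 minutes seated or supine.

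**What the continuous summary covers.** SAP 3.1 uses an 8-point summary: n, mean, SD, median, quartiles, minimum and maximum. Suppose that at one visit an arm's maximum systolic value exceeds 160 mmHg while its upper quartile does not. Assume every planned subject has a value.

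- Active arm, n = 60: at least 1 and at most 0.25 × 60 = 15 subjects exceed the cut-off, that is 1/60 = 1.7% to 15/60 = 25%.
- Placebo, n = 40: at least 1 and at most 0.25 × 40 = 10 subjects, that is 1/40 = 2.5% to 10/40 = 25%.
- If both arms show this pattern, the difference in rates lies anywhere from 1/60 − 10/40 = −23.3 to 15/60 − 1/40 = +22.5 percentage points.

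These bounds use only the quartile and the maximum. The mean and SD narrow them in practice but do not give the count.

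**Visits counted.** SAP 3.1 limits summaries to scheduled or windowed visits unless noted otherwise. Protocol 8.8 lets categorical findings at unscheduled times enter whole-period summaries. Under the SAP as written, an extreme reading between visits would therefore appear only in the listing.

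**The case against.** The strongest defence is that little is lost. The 8-point summary puts each arm's lowest and highest values, and changes, beside placebo at each visit. High heart rates are counted from the ECG. Clinically significant abnormal vital signs may be recorded as adverse events (Protocol 7.2), and infections are summarised as adverse events and by special-interest category. All of this is correct. A reader might infer that outlying heart rates or blood pressures are never compared with placebo; the documents do not support that. What remains is narrower: extremes are shown, but the number of subjects beyond a cut-off is not.

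A reader might also infer an undeclared departure from the protocol, since Protocol 8.1 says "Any changes to the data summaries and analyses outlined in this section will be described in the applicable SAP" and the public copy of SAP 5.1 shows a heading with no text. That does not hold either. Protocol 8.1 does not require an entry under any particular heading, and SAP 3.7.3.2 itself states the revised handling. The blank section may also be an effect of redaction or text extraction, so nothing here rests on it.

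On respiratory rate and temperature, the second sentence of SAP 3.7.3.2 refers to vital signs without restriction, and Protocol 6.4.7 includes both under that term. The drafting is ambiguous, and a firm statement that they have been dropped goes too far.

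**Conclusion.** The point holds as a minor reporting gap. SAP 3.7.3.2 replaces the protocol's counts and percentages with listing flags at identical cut-offs. As a result, the number of subjects per arm beyond the four blood-pressure cut-offs, with heart rate below 40 bpm, or with heart rate 111 to 120 bpm is not tabulated. At Weeks 4 and 8, where no ECG is scheduled, the same applies to heart rates above 120 bpm. Respiratory rate and temperature are unnamed rather than clearly excluded.

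The clinical size cannot be stated. The documents give no baseline blood pressures and no expected rates, and because the cut-offs are absolute values, a given rise crosses them only from a high enough baseline. The range of 1 to 15 subjects in 60 shows how much the planned summary leaves open; it is not an expected count. It assumes full planned arms, and the early termination and site exclusions recorded in the SAP may make the actual numbers smaller. The primary efficacy analysis is not affected.

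**What to change.** In SAP 3.7.3.2:

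1. Add an Induction table by treatment giving the number and percentage of subjects in each Table 8 category, by visit as in Protocol 8.8.5, plus a row for any postbaseline value. State that this row includes unscheduled readings, in line with Protocol 8.8, since SAP 3.1 would otherwise exclude them. Use as denominator the subjects with at least one postbaseline value.
2. For the ATE, give the table by treatment received, with no placebo comparison, because placebo subjects move to TD-1473 80 mg in that phase.
3. Name respiratory rate and body temperature in the summaries of values and changes from baseline.

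If the reduction was intended, record it and the reason in the SAP. The cost is one extra table per period and two extra parameters; the data and the cut-offs already exist.

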3.7.3.3. Electrocardiograms

Descriptive statistics for ECG parameters (heart rate, RR interval, PR interval, QRS interval, QT interval, and QTcF) and changes from baseline values at each assessment time point to the end of study will be presented by treatment group. The QTcF will be calculated using the Fridericia corrections.

Subjects without a postbaseline measurement for a given treatment period will be excluded from the summary statistics (e.g., denominator of the summary statistic) for that time point.

All recorded values by central reader at ECG core lab for the standard 12-lead electrocardiogram parameters will be presented in a by-subject listing.

Categorical Analyses

The number (percentage) of subjects with absolute ECG values and change from baseline in the ranges shown in Table 9 will be presented in Electrocardiogram Categorical Summary by Visit and Time Point.

In addition in the same summary, QTcF will also be summarized by the following categories, Normal (males < 430, females ≤ 450), Borderline (males (> 430, ≤ 450); females (> 450, ≤ 470)) and Prolonged (males > 450, females > 470).

Individual ECG data collected during the study will be presented in a listing. A separate listing of subjects with values of QTcF > 500 msec or an increase > 60 msec will be provided, as necessary.

Figures

Cumulative distribution plots will be provided for maximum change in QTcF at Week 8.

Investigator Assessment of ECG Readings

The investigators' assessment of ECGs as normal, abnormal and clinically significant, or abnormal but not clinically significant will be summarized for baseline and for each visit.

Table 9: ECG Interval Categories

Heart Rate (bpm)	Heart Rate Change from Baseline (bpm)	PR Interval (msec)	PR Percentage Change From Baseline (%)	QRS Interval (msec)	QT _c F (msec)	QT _c F change from Baseline (msec)
> 120	> 20	> 200	> 15	> 120	Males:	≤ 30
> 130	> 30	> 220	> 25		≤ 430	>30, ≤ 60
					> 430	> 60
					> 450	
					> 470	

Heart Rate (bpm)	Heart Rate Change from Baseline (bpm)	PR Interval (msec)	PR Percentage Change From Baseline (%)	QRS Interval (msec)	QT _c F (msec)	QT _c F change from Baseline (msec)
					> 480	
					> 500	
					Females:	
					≤ 450	
					> 450	
					> 470	
					> 480	
					> 500	

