Medication/Medical History	X		X													
Tobacco Use Status			X				X							X	X	
Height	X															
Weight	X		X	X	X		X		X	X	X	X	X	X	X	X
Vital Signs	X		X	X	X		X	X	X	X	X	X	X	X	X	X
12-lead ECG	X		X				X			X	X	X	X	X	X	X
Physical Examination ^F	X		X	X	X		X		X	X	X	X	X	X	X	X
Chest X-ray ^G	X															
Randomization			X ^H													

SCHEDULE OF STUDY PROCEDURES (CONTINUED)

Table 1: Schedule of Study Procedures

Procedures	Screening Period		Treatment Period											Early Study Drug Discontinuation ^A	End of Study ^B (4 weeks post last study drug dose)	
			Induction (Day 1 to Week 12)					Active Treatment Extension (ATE Day 1 to ATE Week 48)								
Study Day/Week	Day -35 to -1		Day 1	W4	W8	W10	W12 ^C	ATE Day 1 ^D	ATE W4	ATE W8	ATE W16 ^E	ATE W24	ATE W36	ATE W48		
	Stage 1	Stage 2														
Hour Post-dose/Window				- 3 to + 5 days	0 to + 7 days	0 to + 3 days	1 – 7 days after W12	- 3 to + 5 days						0 to + 5 days	- 3 to + 5 days	
Study Drug Dispensing			X	X	X			X	X	X	X	X	X			
Study Drug Dosing ^I			X	X	X		X	X	X	X	X	X	X	X		
Dispense Electronic Diary ^J	X															
Corticosteroid Dosing Taper (if applicable) ^K					X		X	X	X							
Telephone Call ^L						X										
Concomitant Medications	-----X-----															
Adverse Event Assessment ^M	-----X-----															
Laboratory Assessments																
Pregnancy Test (females of childbearing potential only) ^N	X		X	X	X		X	X	X	X	X	X	X	X	X	X
FSH ^O	X															

SCHEDULE OF STUDY PROCEDURES (CONTINUED)

Table 1: Schedule of Study Procedures

Procedures	Screening Period		Treatment Period											Early Study Drug Discontinuation ^A	End of Study ^B (4 weeks post last study drug dose)	
			Induction (Day 1 to Week 12)					Active Treatment Extension (ATE Day 1 to ATE Week 48)								
Study Day/Week	Day -35 to -1		Day 1	W4	W8	W10	W12 ^C	ATE Day 1 ^D	ATE W4	ATE W8	ATE W16 ^E	ATE W24	ATE W36	ATE W48		
	Stage 1	Stage 2														
Hour Post-dose/Window				- 3 to + 5 days	0 to + 7 days	0 to + 3 days	1 – 7 days after W12	- 3 to + 5 days						0 to + 5 days	- 3 to + 5 days	
Chemistry, Hematology	X		X	X	X		X		X	X	X	X	X	X	X	X
Urinalysis	X		X	X	X		X		X	X	X	X	X	X	X	X
Overnight Fasting Lipid Panel		X ^P	X	X	X		X		X	X	X	X	X	X	X	X
Viral hepatitis and HIV Serology Panel	X ^Q															
[REDACTED]			■	■	■		■		■	■	■	■	■	■	■	■
Tuberculosis Test (QuantiFeron)	X															
Ileocolonoscopy and Biopsies		X ^R					X ^C									
Fecal Sample for Infectious Studies ^S	X															

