6.3.4. Week 8 (Induction)

Subjects should be instructed to fast from food and non-clear fluids on the evening prior to the Week 8 visit to ensure a minimum 8-hour fast prior to the fasted blood sample collection.

The following procedures will be performed on the Week 8 visit:

- Vital signs
 - Heart rate (HR) and systolic and diastolic blood pressure (BP)
 - Respiratory rate
 - Body Temperature
- Physical examination is to be conducted according to local practice
- Fistula drainage assessment (if applicable) to determine the number of fistula and confirm draining is occurring.
- Weight
- Blood collection

- Hematology
- Serum chemistry
- Overnight fasting lipid panel
- [REDACTED]
- [REDACTED]
- [REDACTED]
- [REDACTED]
- [REDACTED]
- [REDACTED]
- Urine collection
 - Urinalysis
 - Pregnancy test for females of childbearing potential – If urine b-hCG test is positive, confirmation with serum b-hCG test is required
- Disease Assessments
 - CDAI Components
 - Abdominal Pain and Total Stool Frequency Scores
- Perform drug accountability and review subject's compliance with study drug dosing
- Subject dosing in clinic (in the morning before eating)
- Review concomitant medications
- Adverse event assessment (AEs, SAEs, Adverse Events of Special Interest)
- Study drug dispensation and re-review of subject instructions for dosing
- Review diary completion and compliance; counsel subject as needed
- Initiate corticosteroid taper by 2.5 mg per week (Section 6.4.30), for subjects who entered the study on corticosteroids

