6.3.6. Week 12 (Induction)

Subjects should be instructed to fast from food and non-clear fluids on the evening prior to the Week 12 visit to ensure a minimum 8-hour fast prior to the fasted blood sample collection.

The Week 12 ileocolonoscopy and biopsies should be performed on the same day as the Week 12 visit, preferably in the early morning, to permit morning dosing with study drug. However, if not feasible to perform both the ileocolonoscopy and the clinic visit on the same day, the ileocolonoscopy could be performed anytime within 3 days after the Week 12 clinic visit. If the study activities of this Week 12 visit are to be completed over two different visits, the study drug should be continued until the later of the two visits.

The following procedures will be performed at the Week 12 visit:

- Tobacco use status
- Vital signs
 - Heart rate (HR) and systolic and diastolic blood pressure (BP)
 - Respiratory rate
 - Body Temperature
- 12-lead ECG
- Physical examination is to be conducted according to local practice
- Weight
- Blood collection
 - Hematology
 - Serum chemistry
 - Overnight fasting lipid panel
 - [REDACTED]
 - [REDACTED]
 - [REDACTED]
 - [REDACTED]
 - [REDACTED]
 - [REDACTED]
 - [REDACTED]

- Urine collection
 - Urinalysis
 - Pregnancy test for females of childbearing potential – If urine b-hCG test is positive, confirmation with serum b-hCG test is required
- Fecal collection [may be collected within 3 full days (approximately 72 hours) prior to the visit but must precede the start of a bowel preparation if it is to be collected during the same day as the bowel preparation; however, it is preferable that the stool sample be collected during the first bowel movement in the morning]
 - [REDACTED]
- Ileocolonoscopy and Biopsies (Refer to Section 6.4.18)
- Disease Assessments
 - CDAI Components
 - Abdominal Pain and Total Stool Frequency Scores
 - SES-CD Score
 - [REDACTED]
 - [REDACTED]
- Perform drug accountability and review subject's compliance with study drug dosing
- Subject dosing in clinic (in the morning before eating; last dose of Induction study drug)
- Review concomitant medications
- Continue corticosteroid taper by 2.5 mg per week (Section 6.4.30), for subjects who entered the study on corticosteroids (as applicable)
- Adverse event assessment (AEs, SAEs, Adverse Events of Special Interest)
- Review diary completion and compliance; counsel subject as needed

6.3.7. ATE Day 1

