- Continue corticosteroid taper by 2.5 mg per week (Section 6.4.30), for subjects who entered the study on corticosteroids (as applicable)
- Adverse event assessment (AEs, SAEs, Adverse Events of Special Interest)
- Study drug dispensation and re-review of subject instructions for dosing
- Review diary completion and compliance; counsel subject as needed

6.3.9. ATE Week 8

Subjects should be instructed to fast from food and non-clear fluids on the evening prior to the ATE Week 8 visit to ensure a minimum 8-hour fast prior to the fasted blood sample collection.

The following procedures will be performed at the ATE Week 8 visit:

- Vital signs
 - Heart rate (HR) and systolic and diastolic blood pressure (BP)
 - Respiratory rate
 - Body Temperature
- 12-lead ECG
- Physical examination is to be conducted according to local practice
- Weight

- Blood collection
 - Hematology
 - Serum chemistry
 - Overnight fasting lipid panel
 - [REDACTED]
 - [REDACTED]
 - [REDACTED]
 - [REDACTED]
- Urine collections
 - Urinalysis
 - Pregnancy test for females of childbearing potential – If urine b-hCG test is positive, confirmation with serum b-hCG test is required
- Disease Assessments
 - Abdominal Pain and Total Stool Frequency Scores
- Perform drug accountability and review subject's compliance with study drug dosing
- Subject dosing in clinic (in the morning before eating)
- Review concomitant medications
- Confirm corticosteroid taper by 2.5 mg per week (Section 6.4.30) is complete, for subjects who entered the study on corticosteroids (as applicable)
- Adverse event assessment (AEs, SAEs, Adverse Events of Special Interest)
- Study drug dispensation and re-review of subject instructions for dosing
- Review diary completion and compliance; counsel subject as needed

6.3.10. ATE Week 16

Subjects should be instructed to fast from food and non-clear fluids on the evening prior to the ATE Week 16 visit to ensure a minimum 8-hour fast prior to the fasted blood sample collection.

The following procedures will be performed at the ATE Week 16 visit:

- Vital signs
 - Heart rate (HR) and systolic and diastolic blood pressure (BP)
 - Respiratory rate
 - Body Temperature
- 12-lead ECG

- Physical examination is to be conducted according to local practice
- Weight
- Blood collection
 - Hematology
 - Serum chemistry
 - Overnight fasting lipid panel
 - [REDACTED]
- Urine collections
 - Urinalysis

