8.8.6. ECG Data

HR, QT, QTcF, PR, and QRS values at each time point and changes from baseline at each time point after the first dose will be summarized, and counts and percentages will be shown for the following categories:

Table 4: ECG Interval Ranges

Heart Rate (bpm)	Heart Rate Change from Baseline (bpm)	PR Interval (msec)	PR Percent Change From Baseline (%)	QRS Interval (msec)	QTcF (msec)	QTcF change from Baseline (msec)
>120	≥20	□ 200	≥ 15	□ 120	Males:	≤ 30
>130	≥30	□ 220	≥ 25		< 430	>30, ≤ 60
		Optional:			≥ 430	> 60
		≥ 240			≥ 450	
		≥ 260			≥ 470	
		≥ 280			≥ 480	
		≥ 300			≥ 500	
					Females:	
					< 450	
					≥ 450	
					≥ 470	
					≥ 480	
					≥ 500	

In addition, QTcF (msec) will also be summarized by the following categories: Normal (males ≤ 430, females ≤ 450), Borderline (males [$> 430, \leq 450$], females [$> 450, \leq 470$]), and Prolonged (males > 450 , females > 470).

All recorded ECG interval values and ECG assessments will be presented in a by-subject listing. A separate listing of subjects with extreme values or changes, as specified in the SAP (e.g., values of QTcF > 450 msec if male or > 470 msec if female, QTcF increases from baseline > 60 msec) will be provided.

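### The SAP sets its only QTcF figure at Week 8, when no Induction ECG is scheduled, and its QTcF category text leaves a male value of exactly 430 msec unclassified

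*SAP*

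**What the plan says.** **Figure.** SAP 3.7.3.3 (Electrocardiograms) lists one figure item: "Cumulative distribution plots will be provided for maximum change in QTcF at Week 8". SAP Table 6 (Visit Analysis Windows, Section 3.1.3) treats Week 8, Induction Day 49 to 63, and ATE Week 8, ATE Day 49 to 63, as separate visits.

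**ECG schedule.** Protocol Table 1 has an ECG row with ten marks, "12-lead ECG X X X X X X X X X X", set under visit columns that begin "Study Day/Week Day -35 to -1 Day 1 W4 W8 W10 W12 ^C ATE Day 1 ^D". The Week 4, Week 8 and Week 10 cells are blank. The visit lists in Protocol 6.3 say the same thing in prose.

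**Categories.** The SAP's three-level QTcF text starts with "Normal (males < 430, females ≤ 450", followed by Borderline for males above 430 up to 450 and Prolonged above 450. The corresponding sentence in Protocol 8.8.6 starts with "Normal (males ≤ 430, females ≤ 450".

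**The concern.** Safety and tolerability is a primary objective, and ECG change from baseline is a named safety endpoint. A distribution plot is a good way to see outlying QTcF changes by arm, but it needs a visit at which all arms have ECGs by design. The SAP names one at which none do. A programmer who follows the text produces a nearly empty plot. One who notices must choose a visit while preparing the output, and that choice should already be fixed in the plan.

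The category slip is smaller but of the same kind: applied literally, the rule leaves one male value without a class, and the class counts may then not add up to the number of males assessed.

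**Working it through.** There is no planned figure to reproduce. The check compares the schedule, the analysis windows and the category limits.

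**1. Where ECGs are scheduled.** The ECG row in Protocol Table 1 has 16 cells against 16 visit columns. The weight and vital-signs rows align in the same way and do carry a Week 8 mark, so the blank ECG cell is not a column shift. The visit lists give an independent check:

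| Visit (Protocol section) | ECG in Table 1 | ECG in visit list |
|---|---|---|
| Screening Stage 1 (6.3.1.1) | yes | yes |
| Day 1 (6.3.2) | yes | yes |
| Week 4 (6.3.3) | no | no |
| Week 8 (6.3.4) | no | no |
| Week 10 call (6.3.5) | no | no |
| Week 12 (6.3.6) | yes | yes |
| ATE Day 1, ATE Week 4 (6.3.7, 6.3.8) | no | no |
| ATE Weeks 8, 16, 24, 36, 48 (6.3.9 to 6.3.13) | yes | yes |
| End of Study, Early Discontinuation (6.3.14, 6.3.15) | yes | yes |

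The marks total 1 + 1 + 1 + 5 + 2 = 10, as in the table row. The list introduced by "The following procedures will be performed on the Week 8 visit" has no ECG. The one introduced by "The following procedures will be performed at the Week 12 visit" has one, and so does the one introduced by "The following procedures will be performed at the ATE Week 8 visit".

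**2. Scheduled Induction ECG days against the Week 8 window.** Day 1 lies outside Day 49 to 63. Week 12 is nominally Day 84 (SAP Table 6) with a visit window of +3 days (Protocol Section 6), so Day 84 to 87, also outside. Scheduled Induction ECGs in the window: 0.

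**3. What could still land in the window.** The Early Study Drug Discontinuation visit includes an ECG and is held within 5 days after the last dose where possible. To fall in Day 49 to 63 it needs a last dose between about Day 44 (49 − 5) and Day 63. Unscheduled ECGs are also allowed (Protocol 6.1). Any such records would come from a small, selected group.

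**4. Other readings of the sentence.**
- *ATE Week 8.* ECGs exist then, but Protocol Table 2 moves placebo subjects to TD-1473 80 mg in ATE, so no concurrent placebo remains.
- *Maximum up to Week 8.* No post-dose ECG is scheduled before Week 12.
- *Maximum of replicates at Week 8.* Protocol 6.4.8 takes a single ECG per time point.

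**5. Category limits for a male at q = 430 msec.**
- SAP text: q < 430 is false; 430 < q ≤ 450 is false; q > 450 is false. No class applies.
- Protocol 8.8.6 text: q ≤ 430 is true, so Normal.
- SAP Table 9: q ≤ 430 is true, so the value is counted there.
- Protocol Table 4 uses < 430 and ≥ 430, a complementary pair that also leaves no gap.

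Testing every whole value from 350 to 550 msec against the SAP text, 430 is the only male value without a class. The SAP's female limits leave none out. With male Normal at ≤ 430, the count of unclassified values falls from 1 to 0.

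**The case against.** The strongest reply is that very little is lost. SAP 3.7.3.3 plans QTcF values and changes from baseline by treatment at each assessment time point. It also plans a categorical summary by visit that includes changes of ≤ 30, > 30 to ≤ 60 and > 60 msec, and a listing of QTcF above 500 msec or an increase above 60 msec. Week 12 has its own analysis window, so the placebo-controlled data are reported. Protocol 8.8.6 asks for no distribution plot, so no protocol commitment is broken. Table 9 shows which male cut-off was intended. All of this stands, and it rules out three stronger readings:

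- *The randomized QTcF comparison goes unreported.* A reader might infer this, but the Week 12 tables contain it. Only its graphical form is missing.
- *The figure is certain to be empty.* The documents show no scheduled Week 8 ECG, but an early-discontinuation or unscheduled ECG could be windowed there. Nearly empty is as far as they go.
- *Males at 430 msec disappear from the category output.* They drop out of the three-level split only. Table 9 counts them, and a value at the normal/borderline limit cannot hide a prolonged QTcF.

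None of this makes Week 8 a usable visit for the figure or gives a male at 430 msec a class in the SAP text.

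**Conclusion.** Both slips are real and minor. The only figure planned in the SAP's ECG section names a visit with 0 scheduled Induction ECGs, against one scheduled on-treatment ECG visit at Week 12 that covers all three arms. The cost is one supplementary plot; the Week 12 tables and the listing are unaffected. The category text omits exactly one male value, 430 msec, from one of two QTcF classifications. The documents give no basis for estimating how many readings that is.

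The conclusion takes Week 8 in the figure text to mean the Induction visit, as SAP Table 6 labels it; under the ATE reading the figure still lacks a concurrent placebo. The schedule comes from Protocol Table 1 and the visit lists, which agree. The ECG row of the SAP's own schedule was not visible in the text available. No efficacy analysis is touched.

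**What to change.** 1. **Figure.** Replace the Week 8 label with either QTcF change from baseline at Week 12, or the maximum post-baseline QTcF change during Induction, shown by treatment received in Induction on the Safety set. With a single scheduled post-dose ECG, the two differ only for subjects who stop early or have extra ECGs. If the second is chosen, say explicitly that early-discontinuation and unscheduled ECGs within the Induction period (up to last dose + 5 days, SAP 3.1.5.1) count, because SAP 3.1 otherwise limits summaries to scheduled or windowed data. If an ATE figure is also wanted, label it as ATE and as uncontrolled.
2. **Categories.** Change male Normal from < 430 to ≤ 430 in the SAP text, which matches the Protocol 8.8.6 text and SAP Table 9.

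The cost is two short SAP edits and the matching figure and table shells. No new data are needed.
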